APPENDIX 3 - COMMON TOXICITY CRITERIA GRADINGS

Toxicities will be recorded according to the Common Terminology Criteria for Adverse Events (CTCAE), version 4.0. The full CTCAE document is available on the National Cancer Institute (NCI) website, the following address was correct when this version of the protocol was approved: http://ctep.cancer.gov/protocolDevelopment/electronic_applications/ctc.htm

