8.1 Reporting Requirements

8.1.1 Adverse Events

MRI and TURBT are both well documented and widely used procedures. As the safety profiles of both procedures are well characterised, only Serious Adverse Events (SAEs) experienced due to the procedures will be reported.

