8.1.2.1 Expected Serious Adverse Events

We are not expecting any SAEs to occur as a result of participation in this study.

Expected serious adverse events do not need to be reported to the study team.

The following are regarded as expected SAEs for the purpose of study and should not be reported on an SAE form:

- BladderPath
 - Anaemia
 - Bladder discomfort/pain
 - Bladder perforation
 - Bleeding resulting in clot retention
 - Constipation
 - Contrast reaction
 - Diarrhoea
 - Deep Vein Thrombosis (DVT)
 - Fever
 - Gout
 - Haematuria
 - SAEs that are thought to have occurred as a result of the patient's cancer treatment
 - SAEs that are related to symptoms or progression of the patient's cancer

- Insomnia
- Nausea
- Postoperative dysuria
- Prolonged catheterisation
- Skin rash
- Urethral stricture
- Urinary frequency
- Urinary retention
- Urinary tract infection
- Vomiting
- Increased white blood cell count
- SAEs that are related to a pre-existing condition
- Death from cancer, as a result of the patient's cancer treatment or from a preexisting medical condition

This is not an exclusive list and Investigators should only report SAEs which are attributable to the study protocol.

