8.2.1 Site

8.2.1.1 Serious Adverse Events

For more detailed instructions on SAE reporting refer to the SAE Form Completion Guidelines contained in the Investigator Site File (ISF).

AEs defined as serious and which require reporting as an SAE (excluding events listed in Section 8.1.2.1 above) should be reported on an SAE Form. When completing the form, the Investigator will be asked to define the causality and the severity of the AE which should be documented using the CTCAE version 4.0.

On becoming aware that a patient has experienced an SAE, the Investigator (or delegate) must complete, date and sign an SAE Form. The form should be faxed together with a SAE Fax Cover Sheet to the Study Office using one of the numbers listed below as soon as possible and no later than 24 hours after first becoming aware of the event:

To report an SAE, fax the SAE Form with an SAE Fax Cover Sheet to:

[contact]

On receipt the Study Office will allocate each SAE a unique reference number. This number will be transcribed onto the SAE Fax Cover Sheet which will then be faxed back to the site as proof of receipt. If confirmation of receipt is not received within 1 working day please contact the Study Office.

The SAE reference number should be quoted on all correspondence and follow-up reports regarding the SAE. The SAE Fax Cover Sheet completed by the Study Office should be filed with the SAE Form in the ISF.

For SAE Forms completed by someone other than the Investigator, the Investigator will be required to countersign the original SAE Form to confirm agreement with the causality and severity assessments. The form should then be returned to the Study Office in the post and a copy kept in the ISF. Investigators should also report SAEs to their own Trust in accordance with local practice.

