Randomisation Form	Patients details; confirmation of eligibility criteria, result of randomisation pathway allocation, optional consent issues	As soon as possible after randomisation
Baseline Form	Details of baseline assessments	As soon as possible after study entry
Flexible Cystoscopy Form	Details of the procedure	As soon as possible after procedure
TURBT Form	Details of the TURBT procedure	As soon as possible after procedure
MRI Form	Details of the MRI procedure	As soon as possible after procedure
Pathology Form	Pathology details	As soon as pathology report available
Decision to Treat Form	Details of procedures after TURBT/MRI but prior to definitive treatment	As soon as possible after procedures have taken place
Follow-up Form	Details of investigations/treatment during follow-up period	Every 3 months from randomisation up to 12 months, every 6 months from randomisation between 12 months and 24 months and annually thereafter
Recurrence Form	Reporting of any local recurrence or progression	As soon as becoming aware of the recurrence
Death Form	Date and cause of death	Immediately upon notification of patient's death

Deviation Form	Completed in the event of a deviation from the protocol	Immediately upon discovering deviation
Withdrawal Form	Used to notify the Study Office of patient withdrawal from the study	Immediately upon patient withdrawal

Ad hoc forms

Serious Adverse Event Form, Intravesical Form, Systemic Chemotherapy Form, Radiotherapy Form, Cystectomy Form, Palliative Care Form.

This study will use an electronic remote data capture (eRDC) system for completion of the majority of the CRFs, the exception being the Serious Adverse Event form.

The CRFs must be completed, by the investigator or an authorised member of the site research team (as delegated on the Site Signature and Delegation Log) within the timeframe listed above.

Entries on the paper CRF should be made in ballpoint pen, in blue or black ink, and must be legible. Any errors should be crossed out with a single stroke, the correction inserted and the change initialled and dated. If it is not obvious why a change has been made, an explanation should be written next to the change.

Data reported on each form should be consistent with the source data or the discrepancies should be explained. If information is not known, this must be clearly indicated on the form. All missing and ambiguous data will be queried. All sections are to be completed before returning.

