Quality of Life, health economic and patient/carer reported data will be completed on paper forms by the participants and will be regarded as source data for the purposes of this study. These questionnaires will be returned to the Study Office and a copy will not be retained at site.

In all cases it remains the responsibility of the Investigator to ensure that the CRF has been completed correctly and that the data are accurate.

Where paper forms are completed the originals should be sent to the Study Office and a copy filed in the Investigator Site File.

Study forms may be amended by the Study Office, as appropriate, throughout the duration of the study. Whilst this will not constitute a protocol amendment, new versions of the form must be implemented by participating sites immediately on receipt.

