A within study economic evaluation will compare the outcomes and costs for the study comparators over the study follow-up period. First, a cost-consequence analysis will describe all outcomes related to the resource use profiles, costs and health consequences (side-effects, disease progression, recurrences) of the imaging-directed pathway compared with the TURBT directed (standard) pathway for bladder cancer patients. Subsequently, a cost-utility analysis will determine the incremental cost per quality-adjusted life year (QALY) associated with the imaging-directed pathway. Outputs of the economic evaluation will be presented as incremental cost-effectiveness ratios (ICERs); scatterplots of simulated ICER values on cost-effectiveness planes, cost-effectiveness threshold varies across a range of values. Discounting of costs and health consequences will not be required for the within-study economic evaluation. Sensitivity analyses will be used to estimate the between-group differences in mean costs and QALYs. Interaction terms will be used to investigate possible treatment moderators that can identify participant subgroups for whom cost-effectiveness is predictably different, e.g. age, sex, or other relevant participant characteristics.

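### Foreseeable complications of TURBT and MRI have no specified, graded route into the trial database, so the Section 14 side-effect comparison and the SAE count would be incomplete

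*Protocol*

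**What the plan says.** Three places in the Protocol point to side-effects being recorded or compared.

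- Section 14 (Health Economic Evaluation) plans a cost-consequence analysis covering "health consequences (side-effects, disease progression, recurrences) of the imaging-directed pathway compared with the TURBT directed (standard) pathway".
- Section 7.3 (Assessments) lists a review of adverse events at visit 2 (the study procedure) and visit 3 (decision to treat).
- Appendix 3 states: "Toxicities will be recorded according to the Common Terminology Criteria for Adverse Events (CTCAE), version 4.0". It names no form, visit, time window or restriction to serious events.

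Other places set what is reported.

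- Section 8 asks the investigator to assess all adverse events and to document the assessment in source data.
- Section 8.1.1 says that "only Serious Adverse Events (SAEs) experienced due to the procedures will be reported", because the safety profiles of both procedures are well known.
- Section 8.1.2.1 narrows this further: "The following are regarded as expected SAEs for the purpose of study and should not be reported on an SAE form". It also says that expected serious events need not be passed to the study team.
- Section 8.2.1.1 describes the SAE Form, on which "the Investigator will be asked to define the causality and the severity of the AE which should be documented using the CTCAE version 4.0".
- Section 10.1 gives the forms. Table 4 summarises the TURBT Form as "Details of the TURBT procedure", with a similar line for the MRI Form. The ad hoc forms are "Serious Adverse Event Form, Intravesical Form, Systemic Chemotherapy Form, Radiotherapy Form, Cystectomy Form, Palliative Care Form".

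Table 2 lists the number of SAEs as a secondary outcome of the final clinical stage.

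**The concern.** The trial compares a pathway that starts with an operation against one that, for possible MIBC, starts with a scan. Avoiding unnecessary surgery is part of the stated hypothesis, and Table 1 describes TURBT as possibly harmful in MIBC. A comparison of complications by pathway therefore bears directly on the rationale, whichever way it comes out.

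The reporting rules appear to filter out the events that such a comparison needs. Non-serious complications are not reported, and the foreseeable serious ones are classed as expected and kept off the SAE Form. Events left only in the notes of up to 15 centres cannot be reliably recovered at analysis. A later analysis plan cannot repair this, because the gap is in collection.

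**Working it through.** The check is a cross-reading of Sections 2.2, 7.3, 7.7, 8 to 8.2.1.1, 10.1 and 14 and Appendix 3. The plan gives no figure to reproduce.

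**Step 1: what reaches the SAE Form.** An event must be serious, be due to MRI or TURBT (8.1.1), and not be on the 8.1.2.1 list. That list names 22 events and adds four broad categories: effects of cancer treatment, symptoms or progression of the cancer, pre-existing conditions, and deaths from any of these. It is described as not exhaustive.

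**Step 2: worked examples.**

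| Event | Serious? | On the 8.1.2.1 list? | SAE Form? |
|---|---|---|---|
| Bladder perforation at TURBT, prolonging the stay | Yes | Yes | No |
| Clot retention, readmitted | Yes | Yes | No |
| Contrast reaction at MRI, admitted | Yes | Yes | No |
| Urinary tract infection, admitted | Yes | Yes | No |
| Urinary tract infection, treated at home | No | Not relevant | No |
| Dysuria after TURBT, no admission | No | Not relevant | No |
| Serious procedure-related event not on the list | Yes | No | Yes |

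Only the last row is reported. The SAE Form is the one form stated to carry a CTCAE grade (8.2.1.1), so the first six rows have no stated route to a graded record.

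**Step 3: other listed forms.** The TURBT and MRI Forms cover details of the procedure and are due as soon as possible after it. The Decision to Treat Form covers procedures between TURBT or MRI and definitive treatment. The Follow-up Form covers investigations and treatment. The ad hoc treatment forms are named without content. None is stated to hold procedure complications, and none is stated to exclude them. The adverse event review in Section 7.3 names no form for its result. The Schedule of Events has no adverse event row, and Section 7.3 lists no adverse event review at follow-up visits.

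**Step 4: indirect sources.**

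- HES supplies hospital episodes in both arms.
- The Section 14 questionnaires cover hospital and community service use and medication.
- Section 7.7 has concomitant illness recorded at entry and at follow-up.
- The EORTC and EQ-5D-5L questionnaires are first repeated at 3 months.

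These will pick up some of the first six rows, but without a grade and without attribution to the procedure.

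**Step 5: the SAE count.** If Table 2's number of SAEs is counted from SAE Forms, it equals the last row of the table. It would then be a count of unexpected procedure-related events, not of serious complications by pathway.

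**Step 6: size of the contrast in exposure.** With 1:1 allocation, 950 / 2 = 475 patients per arm. If 20-25% have MIBC (Sections 1.1 and 13.2.2), the patients in pathway 2 who could avoid TURBT number at most 475 x 0.20 = 95 to 475 x 0.25 = 119. These are patients, not complications. The Protocol gives no complication rate, so they cannot be turned into a number of missed events.

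**The case against.** The strongest defence has four parts.

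First, Appendix 3 need not conflict with Section 8.1.1. Its heading concerns gradings, and Section 8.2.1.1 applies the same scale to the SAE Form, so it can be read as naming the scale for what Section 8 requires. This stands. A reader might infer a flat contradiction from the appendix alone, and the text does not force that. The narrow reading does not help Section 14, however, because what remains on the SAE Form cannot describe side-effects by pathway.

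Second, a reader might infer that no case report form collects toxicity. The documents do not support that. The SAE Form grades reportable SAEs, and the other forms are only summarised or named, so their fields cannot be read off the Protocol. What stands against the plan is that no route is specified, while the rules that are specified point away from collection.

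Third, a reader might infer that the comparison would have no data, or that the pathways would look alike on harm whatever happened. This also goes too far. Admissions in HES, service use and medication from questionnaires, and concomitant illness give partial data in both arms. They are ungraded and are not a complication record.

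Fourth, limiting reporting is a reasoned choice for two well-known procedures, and non-serious toxicity is not a listed outcome. This is a fair argument for light SAE reporting. It does not explain how a planned between-pathway description of side-effects is to be filled, or why the SAE outcome should leave out the serious complications that can be foreseen.

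**Conclusion.** The point holds in a limited form. Non-serious complications, and the serious ones listed as expected, have no specified, graded route into the trial database. The side-effects part of the Section 14 analysis and the SAE count in Table 2 would therefore be incomplete and would miss the main TURBT and MRI complications.

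The effect is on the description of harms and the cost-consequence analysis. Adherence to pathway 2, time to definitive treatment and clinical progression-free survival are not affected. The size cannot be stated as a number of events. The exposure contrast of at most 95 to 119 avoided TURBTs shows only that the comparison concerns a material group, and it assumes that recruits have the Protocol's 20-25% share of MIBC.

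The conclusion rests on two assumptions: that sites follow 8.1.1 and 8.1.2.1 as written, and that the forms contain no complication fields beyond their stated summaries. If the existing eCRFs already hold such fields, the remaining work is to say so in the Protocol.

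**What to change.** 1. Add a short CTCAE-graded list of the procedure-related events already named in Section 8.1.2.1 to existing eCRFs, for example the Decision to Treat Form and the 3-month Follow-up Form. Use the same list and the same stated time window in both arms, and cover any MRI or TURBT, since some pathway 2 patients will have both. A fixed list asked identically also limits uneven ascertainment in an open-label trial.
2. Report the list by randomised arm, and name it as the source of the side-effects line in Section 14.
3. State that Sections 8.1.1 and 8.1.2.1 govern SAE-form reporting only, and make Appendix 3 consistent with them. Say whether the SAE count in Table 2 includes the serious events listed as expected.
4. If the sponsor prefers not to collect these data, limit Appendix 3 to the grading of reported SAEs, and either remove side-effects from Section 14 or name the partial source to be used.

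The cost is a few fields on existing forms and a few minutes of data entry per patient. Section 10.1 says "Study forms may be amended by the Study Office, as appropriate, throughout the duration of the study" and adds that this is not a protocol amendment. The sentences in 8.1.1, 8.1.2.1, Section 14 and Appendix 3 do need editing in the Protocol itself.
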